7.5.1.2 OS Sensitivity Analyses

Non-Proportional Hazard Assumption

To examine the assumption of proportional hazards in the Cox regression model, in addition to treatment, a time-dependent variable defined by treatment by time interaction will be added into the model. A two-sided Wald Chi-square p-value of less than 0.1 may indicate a potential nonconstant treatment effect. In that case, [REDACTED].

In case non-proportionality cannot be ruled out by the test described above, piecewise hazard ratios (e.g. from 0 to 8 months and after 8months) will be presented together with their corresponding 95% CI.

To investigate the impact of potential non-proportional hazard, the distribution of OS will also be compared using a two-sided weighted log-rank test stratified by the stratification factors, as entered into the IVRS. The weighted log-rank test will use G ($\rho = 0$, $\gamma = 1$) weights, in the terminology of Fleming and Harrington^{14,15}. This p-value will be considered as descriptive.

Additional Sensitivity Analyses

The following OS sensitivity analyses will be performed.

- OS will be compared between treatment groups using a two-sided α (adjusted for the interim) unstratified log-rank test.
- OS will be compared between treatment groups using the strata as determined at baseline (CRF source). This analysis will be performed only if at least one stratification variable at IVRS and at baseline disagrees for at least 10% of the randomized subjects.
- OS will be compared between treatment groups using a two-sided α (adjusted for the interim) stratified log-rank test in the All Treated Subjects population, using arm as randomized. This analysis will be performed only if the proportion of randomized but never treated subjects exceeds 10%.

Estimate of the hazard ratio, its two sided $100(1-\alpha)\%$ CI (adjusted for the interim) and p-value will be presented.

7.5.1.3 Consistency of Treatment Effect on OS in Subsets

To assess consistency of treatment effects in different subsets, a “forest” plot of the OS unstratified hazard ratio (and 95% CI) will be produced for the following subgroups.

- CNS metastases (yes/no). (CRF source).
- Response to Platinum based Therapy (sensitive/resistant) (CRF source).
- Age category ($< 65 - \geq 65$).
- Gender, Race, Region (US vs. Europe vs. Asia vs. Rest of World).
- Baseline ECOG PS.
- Baseline LDH (\leq ULN vs. $>$ ULN).
- Disease Stage at initial diagnosis (extensive vs. limited).
- Time from Initial Disease Diagnosis to Randomization (< 1 year, Other).
- Best response to 1st line (CR/PR vs. SD vs. PD).
- Time from completion of 1st line therapy ($< 3, 3 - 6, > 6$ months).

If subset category has less than 10 subjects per treatment group, HR will not be computed/displayed. Number of events and median OS along with 95% CI will be displayed for each treatment group.

7.5.1.4 Multivariate Analysis

A multivariate stratified Cox model will be fitted to assess the treatment effect on OS when adjusted for potential prognostic factors. The following potential prognostic factors will be included in the model.

- Age category ($< 65 - \geq 65$).
- Gender

- Baseline ECOG PS,
- Disease Stage at initial diagnosis (extensive vs. limited)
- Time from Initial Disease Diagnosis to Randomization (< 1 year, Other).

HR and 95% CI will be provided for treatment variable and all covariates. Descriptive p-values will be provided.

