5 STUDY ASSESSMENTS AND PROCEDURES

5.1 Flow Chart/Time and Events Schedule

Table 5.1-1: Screening Procedural Outline (CA209331)

| Procedure | Screening Visit | Notes |
|---------------------------------------|-----------------|--|
| Eligibility Assessments | | |
| Informed Consent | X | |
| Inclusion/Exclusion Criteria | X | All inclusion/exclusion criteria should be assessed at screening and confirmed prior to first dose |
| Medical History | X | |
| Prior Systemic Therapy | X | |
| Safety Assessments | | |
| Physical Examination | X | |
| Physical Measurements | X | Include Height, Weight, and ECOG performance Status. Within 14 days prior to first dose |
| Vital Signs and Oxygen Saturation | X | Temperature, BP, HR, and O2 saturation by pulse oximetry at rest. Obtain vital signs at the screening visit and within 72 hours prior to first dose. |
| Assessment of Signs and Symptoms | X | Within 14 days prior to first dose |
| Concomitant Medication Collection | X | Within 14 days prior to first dose |
| Laboratory Tests | X | CBC with differential, Chemistry panel including LDH, AST, ALT, ALP, T.Bili, BUN or serum urea level, uric acid, creatinine, Ca, Mg, Na, K, Cl, P, glucose, bicarbonates (optional), albumin, amylase or lipase, TSH (reflex to free T3, free T4 for abnormal TSH result), hepatitis B surface antigen (HBVsAg), and hepatitis C antibody (HCV Ab) or hepatitis C RNA (HCV RNA), within 14 days prior to first dose. Screening labs done within 72 hours prior to first dose can also be used for on treatment lab purposes at Day 1 dosing. |
| ECG, Echocardiogram (LVEF) or MUGA | X | |

Table 5.1-1: Screening Procedural Outline (CA209331)

| Procedure | Screening Visit | Notes |
|---|-----------------|--|
| Pregnancy Test | X | Performed within 24 hours prior to first dose for WOCBP only (serum or urine - local/site) |
| Efficacy/Biomarker Assessments | | |
| Radiographic Tumor Assessment | X | Contrast-enhanced CT of the chest and CT or MRI of abdomen, pelvis, and any other known sites of disease. Brain MRI or CT. Subjects with incidental brain metastases findings at screening will need to undergo radiation treatment first to be eligible. Should be performed within 28 days prior to randomization. Additional sites of known or suspected disease (including CNS) should be imaged at the screening visit and at subsequent on-study assessments. |

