8 STATISTICAL CONSIDERATIONS

8.1 Sample Size Determination

In this study, the primary endpoint of OS will be evaluated for treatment effect at the overall alpha level of 0.05 (two-sided). Approximately 560 subjects will be randomized at a ratio of 1:1 into two arms: Arm A (nivolumab); Arm B (chemotherapy: topotecan or amrubicin). For sample size calculation, non-proportional hazard model with a piecewise exponential distributions in both arms are assumed. Based on published survival curves for topotecan, a 2-piece exponential distribution with an 8-month median OS and taking into account that a limited number of subjects might receive immuno-oncology as subsequent therapy, a conservative 5% 2-year survival rate is assumed for the control arm. A delayed effect for nivolumab with a hazard ratio (HR) of 1 for the first 8 months and an HR of 0.5 thereafter is assumed. The final analysis will take place 34 months after the first patient have been randomized and no formal interim analysis will be conducted. The 560 subjects are expected to be randomized in 18 months, resulting in about 16 months of follow-up for the last subject randomized at the time of the primary analysis. It is anticipated that approximately 480 events will be observed at the time of the analysis, leading to 90% power to detect a difference in overall survival as tested via a log-rank test with a two-sided 0.05 type I error rate. Power calculations were performed using EAST® Software (version 6.4.1).

The decision to incorporate the China subset into the overall population for analysis is the result of a review of the protocol statistical assumptions in comparison to recent data from the CA209032 study in 2L+ SCLC subjects.²⁸ The data from CA209032, which were not available at the time of protocol design, suggest a delayed effect of nivolumab with a non-proportional hazard for survival. Additionally, review of recently generated real-world data for topotecan resulted in updated assumptions for the control arm. Given the updated statistical assumptions, incorporation of the China subset into the study analyses grants adequate statistical power by increasing the study sample size.

| Table 8.1-1: Sample Size Justification | |
|---|---------------------------------------|
| Primary Endpoint | OS |
| Power | 90% |
| Alpha level | 0.05 |
| Sample size | 560 |
| Accrual duration | 18 months |
| Timing of the analysis from randomization of first subject (months) | 34 |

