7.3.2 Demographics and Other Baseline Characteristics

The following baseline characteristics will be summarized by treatment arm as randomized. All baseline presentations identify subjects with missing measurements. Listings will also be provided.

- Age (descriptive statistics).
- Age category (< 65, ≥ 65 - < 75, ≥ 75, ≥ 65).
- Gender, Race/Ethnicity, Region (US/Canada vs. Europe vs. Asia vs. Rest of World).
- Baseline ECOG PS,
- Baseline Weight (kg).
- Baseline LDH (≤ ULN, > ULN)
- Baseline LDH (≤ 2x ULN, > 2x ULN)
- CNS Metastasis (Yes/no)

- Cell type: (SCLC; other)
- Smoking Status (current/former; never smoked; unknown)
- Disease stage: Extensive versus Limited subjects (Source: eCRF)
- All lesions (Investigator Tumor Assessments at Baseline): sites of disease, number of disease sites per subject.
- Target Lesions (Investigator Tumor Assessments at Baseline): Presence of target lesions, site of target lesion, sum of diameters of target lesions.

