7.5 Efficacy

7.5.1 Overall Survival

7.5.1.1 Primary Analysis

The distribution of OS will be compared in two randomized arms at the interim and final analyses via a two-sided, log-rank test stratified by baseline stratification factors, as entered into the IVRS.

The hazard ratio (HR) and the corresponding 100(1- α)% CI (adjusted for the interim) will be estimated in a stratified Cox proportional hazards model using randomized arm as a single covariate.

The OS curves for each treatment group will be estimated using the Kaplan-Meier (KM) product-limit method. Two-sided, 95% confidence intervals for median OS will be constructed based on a log-log transformed CI for the survivor function S(t)¹⁰.

Based on the availability of the data, survival rates at 6, 12, 18, 24, 36, 48 months and at 5 year will also be estimated using KM estimates on the OS curve for each randomized arm. Minimum follow-up must be longer than timepoint to generate the rate. Associated two-sided 95% CIs will be calculated using the Greenwood's formula¹¹ for variance derivation and on log-log transformation applied on the survivor function S(t)

The status of subjects who are censored in the OS Kaplan-Meier analysis will be tabulated for each treatment group using following categories:

- on-study (on-treatment and not progressed, on-treatment progressed, in follow-up);
- off-study: (lost to follow-up, withdraw consent, etc.).

Unless otherwise specified, the primary population will be the all randomized population.

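### The supporting multivariate OS model omits baseline LDH, so no planned overall OS estimate adjusts for a chance LDH imbalance

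*SAP*

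**What the plan says.** SAP 7.5.1.4 fits a stratified Cox model to estimate the treatment effect on OS after adjustment for prognostic factors. The list introduced by "The following potential prognostic factors will be included in the model" has five entries: age category, gender, ECOG performance status, disease stage at initial diagnosis, and time from initial diagnosis. On inference the section says only "Descriptive p-values will be provided".

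LDH appears in three other places:

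- Protocol 5.1, Table 5.1-1, requires at screening "CBC with differential, Chemistry panel including LDH", within 14 days before first dose.
- SAP 7.3.2 tabulates baseline LDH by arm, at ULN and again at twice ULN. It is the only laboratory value in that list. The section adds: "All baseline presentations identify subjects with missing measurements".
- SAP 7.5.1.3 uses LDH (at or below ULN versus above) as a factor in the OS forest plot of unstratified HRs.

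The stratification factors are response to first-line platinum and brain metastases (Protocol 3.1, SAP 2.1). The primary OS hazard ratio comes from a stratified Cox model "using randomized arm as a single covariate" (SAP 7.5.1.1).

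**The concern.** SAP 7.5.1.4 is the one readable place where the plan adjusts the OS effect for covariates beyond the strata. LDH is collected, tabulated and used for subgroups, yet it is balanced by neither the randomisation nor this model. The sensitivity analyses in SAP 7.5.1.2 change the strata source, the population or the log-rank weights; none adds LDH. The forest plot gives an HR within each LDH level but no overall adjusted figure.

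If LDH is prognostic and the arms differ on it by chance, every planned overall OS estimate carries that difference, including the one described as adjusted. Adding LDH only after an imbalance has been seen, in an open-label trial, would look data-driven. What is at stake is the credibility of a supporting estimate, not the primary test.

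**Working it through.** **1. The plan's own power figure.** The documents give no figure for the multivariate model, so the check starts from the primary design. Protocol 8.1 expects about 480 events (482 in Table 8.1-1), "leading to 90% power to detect a difference in overall survival as tested via a log-rank test", with an average HR of about 0.745. By Schoenfeld's formula:

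power = Φ(√(482/4) × |ln 0.745| − 1.96) = Φ(10.98 × 0.2944 − 1.96) = Φ(1.27) = 89.8%.

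This reproduces the stated 90%. The 24-month nivolumab survival also follows: 0.5 × (0.05/0.50)^0.5 = 15.8%, against a stated 16%.

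**2. Size of a chance imbalance.** Assume 50% of subjects above ULN and 280 per arm. The SD of the between-arm difference in that share is √(2 × 0.5 × 0.5/280) = 4.2 points. The edge of the 95% range is 1.96 × 4.2 = 8.3 points.

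**3. Effect of that imbalance on the HR.** Trials were simulated under the planned effect (HR 1 to month 8, then 0.5), 500 per setting. The average HRs are good to about ±0.01.

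| Assumed LDH HR | HR without LDH, imbalance each way | HR with LDH |
|---|---|---|
| 1.5 | 0.72 and 0.77 | 0.74 both ways |
| 2.0 | 0.72 and 0.81 | 0.75 both ways |

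As a hand check, the two extremes should differ by a factor of about exp(2 × 0.083 × ln(LDH HR)). That is 1.07 at 1.5 (simulated 0.77/0.72 = 1.07) and 1.12 at 2.0 (simulated 0.81/0.72 = 1.125).

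**4. Effect on standard error and power over all randomisations.** Inputs: 560 subjects, 1:1, control hazard ln 2/8 to month 8 then ln 10/16, treatment HR 1 then 0.5, uniform 18-month accrual, cutoff at 34 months, no dropout, 50% above ULN, 1000 replicates. Each power figure has a Monte Carlo error of about 1 point. The comparison is a treatment-only Cox model against treatment plus binary LDH.

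| LDH HR (assumed) | HR without → with | SE of log-HR | Power without → with |
|---|---|---|---|
| 1.0 | 0.739 → 0.739 | 0.0908 → 0.0910 | 91.0% → 90.6% |
| 1.3 | 0.747 → 0.744 | 0.0907 → 0.0909 | 90.1% → 90.1% |
| 1.6 | 0.748 → 0.741 | 0.0906 → 0.0909 | 90.0% → 91.5% |
| 2.0 | 0.751 → 0.737 | 0.0905 → 0.0908 | 88.9% → 91.2% |
| 2.5 | 0.759 → 0.737 | 0.0903 → 0.0908 | 87.2% → 91.2% |

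At LDH HR 2.0, a share above ULN of 35% gives 87.7% → 92.1%, and 65% gives 88.9% → 92.1%. Under proportional hazards, which the plan does not assume, the gains are larger: 85.6% → 90.8% at 2.0 and 82.7% → 91.8% at 2.5. In every setting the SE rises, by 0.1 to 0.6%.

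These runs average 500 to 504 events, against 482 planned. The plan does not state its accrual shape or dropout. A 5% annual dropout gives 483 events and an average HR of 0.745, so the gap is not called an error.

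**5. Missing LDH.** If 5% of values are missing and those subjects leave the model, the SE rises by about 1/√0.95 = 1.026, or roughly 3% with the extra covariate (0.0907 → 0.0933 at LDH HR 1.3). Power at LDH HR 1.3 is then 88.5%, against 90.1% without LDH. At LDH HR 2.0 it is 91.0% against 88.9%.

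**The case against.** The strongest reply is that this is a covariate preference. Neither document says LDH is prognostic in relapsed SCLC, or gives its effect or the share above ULN; with no effect or a weak one there is nothing to gain in power. This stands, and the LDH HRs above are assumptions only.

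Subgroup use does not by itself make a covariate: race, region, best response to first line and time since first line are in the forest plot and outside the model too. This stands in part. Best response and time since first line overlap, though not fully, with the platinum-response stratum, and race and region are demographic. LDH is the omitted disease-related factor with no such cover.

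LDH imbalance will be visible in the baseline table, and HRs within LDH levels will be reported. That is true, but a display does not yield an overall adjusted HR.

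The power comparison uses a treatment-only model, whereas the real model is stratified and already holds five covariates. This stands: the increment over that model was not computed and is likely smaller.

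A reader might infer that adding LDH narrows the confidence interval, or that the HR without LDH is simply biased towards 1. Neither follows. The SE of the log-HR rises slightly. Much of the average shift reflects non-collapsibility: the adjusted figure is a conditional HR, which differs from the HR without LDH even when the arms are balanced.

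**Conclusion.** The point holds as a minor, optional improvement. LDH is left out of SAP 7.5.1.4 without explanation and is not a stratification factor, so no overall OS estimate in the unredacted text adjusts for a chance LDH imbalance.

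The main benefit is robustness: at an assumed LDH HR of 2.0 with half the subjects above ULN, an edge-of-range imbalance spreads the HR from 0.72 to 0.81 without LDH and leaves it near 0.75 with it. Any power gain for this model is modest. Under the planned delayed effect with half above ULN, it is about 0 points at LDH HR 1.3, about 2 at 2.0 (2 to 4 across shares of 35 to 65%) and about 4 at 2.5, before allowing for the existing covariates.

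A reader might also infer that the OS conclusion is at risk. The documents do not support that. The model is descriptive, and the primary stratified log-rank test, its alpha, its power and its event count do not change.

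**What to change.** Before database lock, add baseline LDH to the covariates in SAP 7.5.1.4, at or below ULN versus above ULN (the cut-off already used in 7.3.2 and 7.5.1.3), with a missing category so that no subject drops out. State in the same section that the resulting HR is conditional on the listed covariates. If the omission was deliberate, one sentence giving the reason would do instead.

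The missing category matters because the screening window is counted from first dose, SAP 7.3.2 foresees missing baseline values, and 7.5.1.4 has no rule for them.

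The cost is one SAP bullet, no new data collection, and one extra parameter (two if any values are missing) against about 482 events.

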7.5.1.5 Subject Follow-up for OS

The minimum follow-up will be reported. The minimum follow-up is defined as the time interval between the last patient's randomization date and the clinical cutoff date.

The extent of follow-up defined as the time between randomization date and last known date alive (for subjects who are alive) or death date (for subjects who died) will be summarized descriptively (median, min, max) for all subjects randomized.

The currentness of follow-up, defined as the time between last OS contact (i.e., last known date alive or death date) and data cut-off date, will be summarized by treatment group. Subjects who died before data cut-off date will automatically have zero value for currentness of follow-up. For subjects with last known date alive after data cut-off date, they will have zero value for currentness of follow-up as well. The currentness of follow-up will be categorized into the following categories: 0 days, 1-3 months, 3-6 months, 6-9 months, 9-12 months and ≥ 12 months.

7.5.1.6 Follow-up Therapy

Subsequent therapies will be summarized and listed.

- Subsequent Therapy
 - Chemotherapy by drug name
 - Hormonal or biologic therapy by drug name
 - Immunotherapy (anti-PD1 agents, anti-CTLA4 agents and others, by drug name)
 - Tyrosine kinase inhibitor by drug name
 - Other investigational agent by drug name
 - Surgery
 - Radiotherapy
 - Any combination of the above
- By Subject Listing of Subsequent Therapy

7.5.1.7 Analysis of Survival by Tumor Response

Survival by response category will be analyzed by arm using the landmark method¹⁶. Subjects still on study at the landmark time will be separated into two response categories according to whether they have responded before that time. This will assess whether survival from the

landmark depends on the subject's response status at the landmark. Subjects who go off protocol (e.g. subjects who die) before the time of landmark will be excluded from the analysis.

The survival curves from Week 6, Month 4, Month 6, Month 8, Month 12, by response status, for each randomized arm will be produced using the KM product-limit method. Two sided, 95% confidence intervals for median OS will be constructed based on a log-log transformed CI for the survivor function $S(t)$.

7.5.2 Progression Free Survival

7.5.2.1 Primary Analysis of PFS

PFS for each treatment arm will be estimated using Kaplan-Meier product limit method and graphically displayed. A two-sided 95% CI for median duration will be constructed based on a log-log transformed CI for the survivor function $S(t)$ ^{9,10}.

The comparison of PFS distribution will be performed via a stratified log-rank test at two-sided, 5% level. In addition, the stratified hazard ratios between treatment groups will be provided along with the 95% CI.

PFS rates at 6, 12, 18, 24, 36, 48 months and at 5 year will also be estimated using KM estimates on the PFS curve for each randomized arm. Minimum follow-up must be longer than or equal to timepoint to generate the rate. Associated two-sided 95% CIs will be calculated using the Greenwood's formula¹¹.

The source of progression (death vs. progression) will be summarized by treatment group.

The status of subjects who are censored in the PFS Kaplan-Meier analysis will be tabulated for each treatment group using following categories:

- Never treated
- On-study (on treatment, in follow-up)
- Off-study: (lost to follow-up, withdrew consent, other).
- Received subsequent anti-cancer therapy
- No baseline tumor assessment

To assess consistency of treatment effect on PFS in different subsets, a “forest” plot of the PFS unstratified hazard ratio (and 95% CI) will be produced for the same variable as in the OS analysis.

7.5.2.2 Sensitivity Analyses of PFS

Sensitivity analyses of PFS will also be performed using the following modification of PFS primary definition.

- PFS will be compared between treatment groups *using the strata as determined at baseline* (CRF source). This analysis will be performed only if at least one stratification variable at IVRS and at baseline disagrees for at least 10% of the randomized subjects.

- *PFS accounting for assessment after subsequent therapy* subjects will be defined similarly to the primary definition except that events (progression or death) and tumor assessments that occurred on or after subsequent anticancer therapy will be taken into account.
- *PFS accounting for missing tumor assessment prior to PFS event (progression or death)*. This analysis will be performed only if at least 20% of events have missing prior tumor assessment. It will apply the following restriction to the primary definition: If the elapsed time between the PFS event and the last on-study assessment immediately prior to the event (or randomization date if no on-study scan) is two or more missed visits (more than 12 weeks + 10 days), the subject will be censored at his last tumor assessment prior to the PFS event (or randomization date if no on-study scan).
- *PFS accounting for assessment after on-treatment palliative radiotherapy*. This analysis is similar to the primary analysis except that no censoring will occur for on-treatment palliative radiotherapy.

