Subjects will be evaluated for tumor response beginning 6 weeks from the date of first dose (± 5 days), then every 6 weeks (± 5 days) thereafter up to 30 weeks, then it will be every 12 weeks (± 5 days) until disease progression (or until discontinuation of study drug in subjects receiving nivolumab beyond progression), lost to follow-up, withdrawal of study consent, or the study ends. See Table 5.4-1 for a schedule of tumor assessments. Tumor assessments for all subjects should continue as per protocol even if dosing is delayed. Tumor measurements should be made by the same investigator or radiologist for each assessment whenever possible.

Tumor imaging assessments for ongoing study treatment decisions will be completed by the investigator using RECIST 1.1 criteria; see [Appendix 2](#).

| Table 5.4-1: Schedule of CT/MRI Tumor Assessments(CA209331) | | | |
|--|-----------------------------|--|--------------------------|
| Time On Study | Assessment Frequency | Assessment Week (Day 1 of Week Shown) | Assessment Window |
| Baseline | | Week 0 | - 28 days |
| Between Week 6 and Week 30 | Every 6 weeks | 6, 12, 18, 24, 30 | ± 5 days |
| Beyond Week 30 | Every 12 weeks | 42, 54, 66+ | ± 5 days |

Note: Tumor assessments will continue until disease progression (or until discontinuation of study drug in subjects receiving nivolumab beyond progression), lost to follow-up, withdrawal of study consent, or the study ends.

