2 STUDY DESCRIPTION

2.1 Study Design

This is a randomized, open-label, two-arm, multicenter, Phase 3 study in adult subjects with relapsed SCLC treated with prior platinum-based, first-line chemotherapy. Subjects must have had at least 4 cycles of platinum-based, first-line chemotherapy, or if they received less than 4 cycles, they must have had a best overall response (BOR) of a partial or complete response after completion of chemotherapy.

Approximately 480 subjects will be randomized in a 1:1 ratio to treatment with either nivolumab (Arm A) or chemotherapy (either topotecan or amrubicin, Arm B) in the Global Population. In addition, this study includes a cohort of at least 78 additional randomized patients from China (~16% of the global number of randomized subjects). The primary population for safety and efficacy analysis will include subjects from the Global Population as well as subjects from the additional Chinese cohort, leading to a total sample size of about 560 subjects.

Subjects will be stratified according to the following factors:

- Response to first-line platinum based treatment: platinum sensitive (progression-free interval ≥ 90 days after completion of platinum therapy) vs platinum resistant (progression-free interval < 90 days after completion of platinum therapy)
- Brain metastases at baseline: yes vs. no.

On-study tumor assessments will begin at Week 6 post randomization (± 5 days) and be performed every 6 weeks (± 5 days) until Week 30. After Week 30, tumor assessments will be performed every 12 weeks (± 5 days) until disease progression (or until discontinuation of study drug in subjects receiving nivolumab beyond investigator-assessed progression) lost to follow-up, withdrawal of study consent, or the study ends.

Enrollment will end after approximately 560 subjects have been randomized (including ~78 additional subjects in China).

[figure not shown]
The primary endpoint of the study is OS.

The study design schematic is presented in [Figure 2.1-1](#).

Accrual duration is expected to be approximately 18 months; overall study duration will be approximately 34 months (18 months accrual + minimum follow up of 16 months). The study will end when analysis of survival is complete. Additional survival follow-up may continue for up to 5 years from the time of this analysis.

A DMC will be utilized to provide general oversight and safety considerations for this study, CA209331.

Figure 2.1-1: Study Schematic

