4.2 Secondary Endpoints

4.2.1 *Progression - Free Survival*

Progression-free survival (PFS) is defined as the time from randomization to the date of the first documented tumor progression as determined by the investigator using RECIST 1.1 criteria or death due to any cause. Clinical deterioration in the absence of unequivocal evidence of progression (per RECIST 1.1) is not considered progression for purposes of determining PFS. Subjects who die without a reported prior progression will be considered to have progressed on the date of their death. Subjects who did not progress or die will be censored on the date of their last evaluable tumor assessment. Subjects who did not have any baseline or on-study tumor assessments and did not die will be censored on the date they were randomized. Subjects who received any subsequent anti-cancer therapy (including on-treatment palliative RT of non-target bone lesions) without a prior reported progression will be censored at the last evaluable tumor assessment prior to or on the date of initiation of the subsequent anti-cancer therapy.

Table 4.2.1-1: Censoring Scheme for Primary Definition of PFS

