The p-values from sensitivity analyses for efficacy endpoints are for descriptive purpose only and not adjusted for multiplicity.

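### The PFS missed-scan analysis equates two missed visits with a fixed 94 days, so once scans move to every 12 weeks it can censor an event after one missed scan

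*SAP*

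**What the plan says.** One of the PFS sensitivity analyses in SAP 7.5.2.2 deals with events that follow missing tumor assessments. It measures the time from the last on-study scan (or from randomization if there was none) to the event. If that time is "two or more missed visits (more than 12 weeks + 10 days), the subject will be censored at his last tumor assessment". No other limit is given for later follow-up.

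SAP 2.1 has scans "performed every 6 weeks (± 5 days) until Week 30" and then a longer interval: "After Week 30, tumor assessments will be performed every 12 weeks (± 5 days"). Protocol Table 5.4-1 gives the same schedule by week: "Between Week 6 and Week 30 | Every 6 weeks | 6, 12, 18, 24, 30 | ± 5 days", then "Beyond Week 30 | Every 12 weeks | 42, 54, 66+ | ± 5 days".

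Two statements limit how much the analysis can affect. On when it is run: "This analysis will be performed only if at least 20% of events have missing prior tumor assessment". On its status, SAP 7.1 says: "The p-values from sensitivity analyses for efficacy endpoints are for descriptive purpose only and not adjusted for multiplicity".

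**The concern.** The rule is stated twice in one sentence, as a count of visits and as a number of days. The two agree only while scans are 6 weeks apart. Once they are 12 weeks apart, a gap of more than 94 days no longer implies two missed visits.

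The analysis is meant to show whether the PFS result survives when events seen only after a long unobserved stretch are set aside. For late events it would apply a stricter rule than the one described. For example, a progression found at Week 54 after a single missed scan at Week 42 becomes a censoring at Week 30. One event and 24 weeks of time at risk are lost. A reader told that only events after two missed visits were removed could misread a difference from the primary PFS result.

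Deaths are exposed too, because of the primary definition in SAP 4.2.1: "Subjects who die without a reported prior progression will be considered to have progressed on the date of their death". The subjects affected are those still event-free and followed at about Week 24 or later. Protocol 1.1.3.5 expects longer responses on nivolumab than on topotecan, so the effect could differ by arm, but the documents do not allow this to be quantified.

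**Working it through.** **Inputs.** Scan days from Protocol Table 5.4-1: Weeks 6, 12, 18, 24, 30, 42, 54, 66 are days 42, 84, 126, 168, 210, 294, 378, 462, each ± 5 days. The gap between two in-window scans therefore varies by ± 10 days. The limit comes from SAP 7.5.2.2. The 6-weekly brain MRI for subjects with a history of brain metastasis (Protocol 5.4) is not counted here.

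**The plan's figure.** 12 weeks + 10 days = 12 × 7 + 10 = 94 days. With 6-week scans, two intervals plus two windows give 2 × 42 + 2 × 5 = 94, an exact match. With 12-week scans the same construction gives 2 × 84 + 2 × 5 = 178.

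**One scan missed, progression found at the next scheduled scan.**

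| Last scan | Missed | Progression at | Nominal gap (days) | Range (days) | Result at 94 days |
|---|---|---|---|---|---|
| Week 6 | Week 12 | Week 18 | 126 − 42 = 84 | 74–94 | kept |
| Week 12 | Week 18 | Week 24 | 168 − 84 = 84 | 74–94 | kept |
| Week 18 | Week 24 | Week 30 | 210 − 126 = 84 | 74–94 | kept |
| Week 24 | Week 30 | Week 42 | 294 − 168 = 126 | 116–136 | always censored |
| Week 30 | Week 42 | Week 54 | 378 − 210 = 168 | 158–178 | always censored |
| Week 42 | Week 54 | Week 66 | 462 − 294 = 168 | 158–178 | always censored |

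**Two scans missed on the 6-week schedule.** Week 6 to Week 24 is 168 − 42 = 126 days (116–136), always censored. The rule works as labelled there.

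**Death or unscheduled progression, last scan on time.** A second visit has been missed only when its window closes without a scan.
- Last scan Week 24 (day 168): the Week 42 window closes on day 299, and 299 − 168 = 131. Events on days 95–131 after the scan are censored with one visit missed, a span of 37 days.
- Last scan Week 30 (day 210): the Week 54 window closes on day 383, and 383 − 210 = 173. Events on days 95–173 are censored with one visit missed, a span of 79 days. The same holds for later scans.
- Events up to day 94 are kept in both cases.

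**Edge error on the 6-week schedule, for comparison.** With the Week 6 scan on day 42 and Weeks 12 and 18 missed, the second window closes on day 131, which is 131 − 42 = 89 days later. A death on days 90–94 is kept although two visits were missed, an error of 5 days. If the Week 6 scan was on day 37 or day 47, the error is 0 days (131 − 37 = 94) or 10 days (131 − 47 = 84).

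**Limits that would match the wording.** Nominal time to the second missed scan plus 10 days: 94 days if the last scan was at Week 18 or earlier, 126 + 10 = 136 days if at Week 24, and 168 + 10 = 178 days if at Week 30 or later.

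**Who is exposed.** The documents give no PFS assumption. Assuming exponential PFS with a median between 1.5 and 6 months, the event-free proportion is 2^(−t/median), with t = 168/30.4375 = 5.52 months at Week 24 and 210/30.4375 = 6.90 months at Week 30. That gives about 8% to 53% at Week 24 and 4% to 45% at Week 30. Only those who then miss a scan are affected, and that fraction is unknown.

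**The case against.** The strongest reply is that 94 days need not come from 6-week scans, since the SAP gives no derivation. It also equals one 12-week interval plus both windows (84 + 10), the longest gap between consecutive in-window scans after Week 30 (day 205 to day 299). A subject who attends every scan in window is therefore never censored when progression is found at a scheduled scan. On this view the number is a sound uniform tolerance for unobserved time and only the label is loose. Counting visits would accept gaps of up to 136 or 178 days late on, which is arguably too lenient, and would require a rule for out-of-window scans.

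Much of this is fair. The 6-week origin is an inference, the number can be programmed without ambiguity, and a fixed gap is a legitimate design. But if 94 days is read as one 12-week interval plus windows, exceeding it after Week 30 signals one missed visit, so the label is still wrong. A programmer who follows the words and one who follows the number would build different datasets.

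A second reply is that 6-weekly brain MRI shortens the gaps for subjects with a history of brain metastasis. If a brain MRI alone counts as an on-study assessment, the gaps above do not apply to subjects who had one in between. The SAP does not say whether it counts. The finding stands for everyone else.

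The third reply, that the analysis is conditional, descriptive and outside the testing hierarchy, is correct. It limits the severity but does not remove the inconsistency.

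**Conclusion.** The concern holds, as a minor point. For events whose last scan is at Week 24 or later, the stated number does not do what the stated words say. Progression found at the next scheduled scan after one missed scan is always censored, with gaps of 116–136 or 158–178 days against a limit of 94. Deaths and unscheduled progressions are affected only when they fall in the windows derived above. The mismatch of up to 79 days is far larger than the 0 to 10 days of edge error on the 6-week schedule.

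This rests on scans done within their windows (on time for the death and unscheduled-progression figures) and on brain-only MRI not counting as a tumor assessment. Primary PFS, OS and the hierarchical tests are untouched. Neither the number of events affected nor the direction by arm can be derived from the documents.

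**What to change.** Replace the fixed limit in SAP 7.5.2.2 with a count: censor when two or more scheduled assessments in Protocol Table 5.4-1 have passed, windows closed and no scan done, between the last scan (or randomization) and the event. State whether an out-of-window scan counts as missed and whether a brain-only MRI counts as an assessment, and use the same definition of missing for the 20% trigger. Limits of 94, 136 or 178 days according to the last scan would be a close alternative.

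If a uniform maximum gap is what is wanted, keep 94 days, remove the reference to missed visits, and describe the analysis as a fixed-gap rule.

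The cost is a short edit to the SAP and a small programming change. No new data are needed.
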